|-----------------|-----------------------|--|-------------------|-----------------------|--|-------------------|
| Age
(months) | Underweight:
BMI < | Healthy weight/
Overweight:
BMIT • I | Obese :
BMI >= | Underweight:
BMI < | Healthy weight/
Overweight:
BMTI • I | Obese :
BMI >= |
| 203.5           | 17.65613              | 17.65613;28.19937                          | 28.19937          | 17.17981              | 17.17981;29.57491                          | 29.57491          |
| 204.5           | 17.70284              | 17.70284;28.25676                          | 28.25676          | 17.21234              | 17.21234;29.6335                           | 29.6335           |
| 205.5           | 17.74935              | 17.74935;28.3142                           | 28.3142           | 17.24429              | 17.24429;29.69187                          | 29.69187          |
| 206.5           | 17.79564              | 17.79564;28.37173                          | 28.37173          | 17.2756               | 17.2756; 29.75004                          | 29.75004          |
| 207.5           | 17.8417               | 17.8417;28.42937                           | 28.42937          | 17.30628              | 17.30628; 29.80802                         | 29.80802          |
| 208.5           | 17.88751              | 17.88751; 28.48716                         | 28.48716          | 17.3363               | 17.3363;29.86584                           | 29.86584          |
| 209.5           | 17.93306              | 17.93306;28.54513                          | 28.54513          | 17.36564              | 17.36564;29.92352                          | 29.92352          |
| 210.5           | 17.97834              | 17.97834; 28.6033                          | 28.6033           | 17.39427              | 17.39427;29.98109                          | 29.98109          |
| 211.5           | 18.02333              | 18.02333;28.66171                          | 28.66171          | 17.42218              | 17.42218;30.03857                          | 30.03857          |
| 212.5           | 18.06802              | 18.06802; $28.72041$                       | 28.72041          | 17.44935              | 17.44935;30.09599                          | 30.09599          |
| 213.5           | 18.11239              | 18.11239; $28.77941$                       | 28.77941          | 17.47576              | 17.47576;30.15337                          | 30.15337          |
| 214.5           | 18.15644              | 18.15644; $28.83875$                       | 28.83875          | 17.50137              | 17.50137; 30.21074                         | 30.21074          |
| 215.5           | 18.20014              | 18.20014; $28.89848$                       | 28.89848          | 17.52618              | 17.52618;30.26812                          | 30.26812          |
| 216.5           | 18.24349              | 18.24349; $28.95862$                       | 28.95862          | 17.55015              | 17.55015;30.32554                          | 30.32554          |
| 217.5           | 18.28646              | 18.28646; 29.01921                         | 29.01921          | 17.57328              | 17.57328;30.38304                          | 30.38304          |
| 218.5           | 18.32904              | 18.32904; 29.0803                          | 29.0803           | 17.59553              | 17.59553;30.44063                          | 30.44063          |
| 219.5           | 18.37122              | 18.37122;29.14191                          | 29.14191          | 17.61689              | 17.61689; 30.49835                         | 30.49835          |
| 220.5           | 18.41299              | 18.41299;29.20409                          | 29.20409          | 17.63733              | 17.63733;30.55623                          | 30.55623          |
| 221.5           | 18.45432              | 18.45432;29.26687                          | 29.26687          | 17.65683              | 17.65683; 30.6143                          | 30.6143           |
| 222.5           | 18.4952               | 18.4952;29.3303                            | 29.3303           | 17.67537              | 17.67537; 30.6726                          | 30.6726           |
| 223.5           | 18.53562              | 18.53562;29.39442                          | 29.39442          | 17.69293              | 17.69293;30.73114                          | 30.73114          |
| 224.5           | 18.57556              | 18.57556; 29.45926                         | 29.45926          | 17.70948              | 17.70948;30.78997                          | 30.78997          |
| 225.5           | 18.615                | 18.615; 29.52487                           | 29.52487          | 17.725                | 17.725;30.84911                            | 30.84911          |
| 226.5           | 18.65393              | 18.65393;29.5913                           | 29.5913           | 17.73946              | 17.73946; 30.90861                         | 30.90861          |
| 227.5           | 18.69233              | 18.69233; 29.65857                         | 29.65857          | 17.75286              | 17.75286; 30.96849                         | 30.96849          |
| 228.5           | 18.73019              | 18.73019; 29.72674                         | 29.72674          | 17.76515              | 17.76515; 31.0288                          | 31.0288           |
| 229.5           | 18.76748              | 18.76748; 29.79585                         | 29.79585          | 17.77632              | 17.77632; 31.08956                         | 31.08956          |
| 230.5           | 18.8042               | 18.8042; 29.86595                          | 29.86595          | 17.78635              | 17.78635; 31.15082                         | 31.15082          |
| 231.5           | 18.84031              | 18.84031; 29.93707                         | 29.93707          | 17.79521              | 17.79521;31.21261                          | 31.21261          |
| 232.5           | 18.87581              | 18.87581; 30.00927                         | 30.00927          | 17.80288              | 17.80288; 31.27496                         | 31.27496          |

|                 |                       | Boys                                      |                   |                       | Girls                                       |                   |
|-----------------|-----------------------|---|-------------------|-----------------------|---|-------------------|
| Age
(months) | Underweight:
BMI < | Healthy weight/
Overweight:
BMI   ; | Obese :
BMI >= | Underweight:
BMI < | Healthy weight/
Overweight:
BMI [ ; [ | Obese :
BMI >= |
| 233.5           | 18.91068              | 18.91068;30.08258                         | 30.08258          | 17.80934              | 17.80934;31.33793                           | 31.33793          |
| 234.5           | 18.94489              | 18.94489;30.15706                         | 30.15706          | 17.81456              | 17.81456;31.40154                           | 31.40154          |
| 235.5           | 18.97844              | 18.97844; 30.23276                        | 30.23276          | 17.81852              | 17.81852;31.46583                           | 31.46583          |
| 236.5           | 19.01129              | 19.01129;30.30971                         | 30.30971          | 17.82119              | 17.82119;31.53085                           | 31.53085          |
| 237.5           | 19.04343              | 19.04343; 30.38797                        | 30.38797          | 17.82256              | 17.82256;31.59664                           | 31.59664          |
| 238.5           | 19.07484              | 19.07484;30.46758                         | 30.46758          | 17.82259              | 17.82259;31.66324                           | 31.66324          |
| 239.5           | 19.10551              | 19.10551; 30.54859                        | 30.54859          | 17.82127              | 17.82127;31.73069                           | 31.73069          |
| 240             | 19.12055              | 19.12055;30.58964                         | 30.58964          | 17.82009              | 17.82009; 31.76474                          | 31.76474          |
| 240.5           | 19.1354               | 19.1354;30.63106                          | 30.63106          | 17.81856              | 17.81856;31.79903                           | 31.79903          |
|                 |                       |   |                   |                       |   |                   |

Cl

# 8.4 Adverse Events of Special Interest – Remote Spread of Effects

The following list of MedDRA PT names and codes (version 20.0) has been defined to identify any events which may possibly represent a remote spread of effect:

| PT Name                        | PT Code  |
|--------------------------------|----------|
| Accommodation disorder         | 10000389 |
| Areflexia                      | 10003084 |
| Aspiration                     | 10003504 |
| Botulism                       | 10006041 |
| Bradycardia                    | 10006093 |
| Bulbar palsy                   | 10006542 |
| Constipation                   | 10010774 |
| Cranial nerve palsies multiple | 10011314 |

| Cranial nerve paralysis                       | 10061908 |
|---|----------|
| Diaphragmatic paralysis                       | 10012725 |
| Diplopia                                      | 10013036 |
| Dry mouth                                     | 10013781 |
| Dysarthria                                    | 10013887 |
| Dysphagia                                     | 10013950 |
| Dysphonia                                     | 10013952 |
| Dyspnoea                                      | 10013968 |
| Extraocular muscle paresis                    | 10015829 |
| Eyelid function disorder                      | 10061145 |
| Eyelid ptosis                                 | 10015995 |
| VIIth nerve paralysis (Low Level Term (LLT))  | 10050040 |
| Facial paresis                                | 10051267 |
| Hemiparesis                                   | 10019465 |
| Hypoglossal nerve paresis                     | 10067129 |
| Hyporeflexia                                  | 10021089 |
| Hypotonia                                     | 10021118 |
| IIIrd nerve paresis                           | 10054202 |
| Ileus paralytic                               | 10021333 |
| IVth nerve paresis                            | 10054201 |
| Monoparesis                                   | 10027925 |
| Muscular weakness                             | 10028372 |
| Paralysis                                     | 10023372 |
| Paralysis
Paralysis flaccid ( LLT ) | 10033809 |
|   | 10033885 |
| Paresis                                       | 10033985 |
| Paresis cranial nerve                         | 10061911 |
| Pelvic floor muscle weakness                  | 10064026 |
| Peripheral nerve palsy                        | 10058530 |
| Peripheral paralysis                          | 10054808 |
| Pneumonia aspiration                          | 10035669 |
| Pupillary reflex impaired                     | 10037532 |
| Quadriparesis                                 | 10049680 |
| Respiratory arrest                            | 10038669 |
| Respiratory depression                        | 10038678 |
| Respiratory depression                        | 10038695 |
| Speech disorder                               | 10041466 |
| Trigeminal nerve paresis                      | 10068008 |
| Uringry retention                             | 10046555 |
| Vision blurred                                | 10047513 |
| Vocal cord paralysis                          | 10047674 |
| Vocal cord paresis                            | 10049234 |
| Neuromuscular toxicity                        | 10062284 |
| Paralysis recurrent larvngeal nerve           | 10033830 |
| Respiratory distress                          | 10038687 |
| Respiratory paralysis                         | 10038708 |
| Respiratory paratysis                         | 10030/00 |

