2.1 Disease Review

Cerebral palsy (CP) describes a group of permanent disorders of the development of movement and posture, causing activity limitation, that are attributed to nonprogressive disturbances that occurred in the developing foetal or infant brain. The motor disorders of CP are often accompanied by disturbances of sensation, perception, cognition, communication, and behaviour, by epilepsy, and by secondary musculoskeletal problems leading to posture and gait impairment, and limb deformities [9]. The reported prevalence of CP is between 1.5 and 3 cases per 1000 live births [10, 11]. The bilateral form of CP (which includes diplegia, triplegia and quadriplegia) predominates, followed by unilateral (hemiplegia), which accounts for about one quarter to one third of all spastic cases [9, 11].

Cerebral palsy is an upper motor neuron disorder, which can present clinically with different combinations of positive and negative phenomena. The positive phenomena of the syndrome include among others spasticity, increased tendon reflexes, clonus and muscle co-contraction. The negative phenomena are muscle weakness, impaired motor control, loss of skilled movements and easy fatigability. In children, the positive phenomena of CP are a major cause of disability and considered more amenable to treatment [12].

Ninety percent (90%) of subjects with CP suffer from spastic hypertonia. Spasticity is a motor disorder, characterised by an increase in velocity dependant stretch reflexes, with exaggerated tendon reflexes, resulting from hyper-excitability of the stretch reflex, as one of the manifestations of the upper motor neuron syndrome [13]. The increased muscle tone in spasticity leads to muscle contractures, initially dynamic and later fixed, followed by shortening of ligaments, fascias and joint capsules, and eventually joint deformities and instabilities.

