8 STUDY EVALUATIONS

For the timing of assessments during the study, refer to the study schedules in Appendix 1.

The following examinations will be performed at screening or baseline only.

Evaluation of Cerebral Palsy

At baseline, the subjects CP will be evaluated by:

- A diagnosis of CP as defined by Rosenbaum [9].
- The presence of spastic hemiparesis, paraparesis, diparesis, or tetraparesis.
- Presence and intensity of severe athetoid or dystonic movements in the targeted upper limb.
- Evaluation of hypertonia to capture baseline dystonic/spastic characteristic using the Hypertonia Assessment Tool [45, 46].
- Planned or completed surgery of the upper limbs.
- History of injection of alcohol and/or phenol.

Neurological Examination

A neurological examination will be performed by the Investigator at screening. The neurological examination will include:

- Strength.
- Deep tendon reflexes (biceps and triceps only).

Gross Motor Function Classification System

The GMFCS is a five-level classification that differentiates children with CP based on the child's current gross motor abilities, limitations in gross motor function, and need for assistive technology and wheeled mobility [44]. Further details will be provided in the study manual.

Manual Ability Classification System

The MACS is a five-level classification that assesses how children with CP use their upper limb for handling objects in their daily life [18, 19]. Further details are provided in Appendix 7. Mini-MACS is the same scale adapted to children between 2 and 4 years of age (4 years excluded). For subjects already recruited in the study at the time of protocol amendment approval, the MACS (or mini-MACS) will be assessed retrospectively, based on source data obtained over 2 months prior to randomization into the study. The investigator will document the assessment at the date it is assessed both in the subjects file and in the eCRF (appendix

pages). In case it is not possible to assess MACS (or mini-MACS) the data will be noted as not applicable in the eCRF.

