10.1.4 Adverse Events of Special Interest

The effects of Dysport and all BTX products may spread from the area of injection to produce symptoms consistent with BTX effects. These symptoms have been reported hours to weeks after injection. Remote spread of toxin that affects swallowing and breathing can be life threatening, and there have been reports of death. The risk of symptoms is increased in subjects who have underlying conditions (e.g. disorders of the neuromuscular junction) that would predispose them to these symptoms. Dysport is contraindicated in individuals with known hypersensitivity to any BTX preparation or to any of the components in the formulation. Adverse events of special interest (AESIs) for Dysport are AEs that suggest a possible remote spread of effect of the toxin or hypersensitivity. A list of preferred terms of AESIs is provided in the Statistical Analysis Plan. All AEs will be monitored by the sponsor to determine if they meet the criteria of AESIs. These AESIs will be further analysed to determine if there is a plausible possibility that they represent distant spread of toxin or hypersensitivity. In order to perform the analysis, variables including alternate aetiology (medical history, concomitant medication, or diagnosis which could account for the symptoms), location of Dysport administration, and temporal relationship to Dysport administration will be considered by the sponsor.

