Adverse events of special interest (AESIs) for Dysport are TEAEs that suggest a possible remote spread of effect of the toxin or events suggestive of hypersensitivity like reactions. TEAEs due to possible remote spread of the effects of Dysport will be identified using the list of MedDRA PTs compatible with the mechanism of action of BTX-A and based on the recommendations from the Committee for Medicinal Products for Human Use (CHMP) and the Food and Drug Administration (FDA). TEAEs potentially representing hypersensitivity reactions will be identified using the Standardised MedDRA Query (SMQ) (narrow search query) for hypersensitivity reactions. A list of MedDRA PTs, used to identify any potential AESI, is provided in Appendix 8.4 of the SAP.

All TEAEs identified using the search strategy described above will be medically evaluated during the study, before the database lock and unblinding, by the sponsor to identify events which could possibly represent 'remote spread of effect of toxin', or which are suggestive of 'hypersensitivity reactions' due to study treatment administration. Cases will be excluded if they are confounded by presence of alternative clinical etiologies (medical history, concomitant medication or diagnosis which could account for the symptoms); if they are considered to be local effects instead of distant spread as judged by the site of injection; the time period between the last study treatment administration and event onset is not in accordance with the expected mechanism of action; or due to insufficient information/evidence to make an assessment.

In the TLFs, only the final list of AESIs confirmed by the sponsor as "a possible remote spread event" or "hypersensitivity reactions" will be taken into account.

Across all Treatment Cycles 1, 2, 3, and 4 an overall summary table of all AEs will be presented by treatment group for **study limb dose** (administered in the specified Treatment Cycle using the dose groups specified in Section 3.2.1.2), summarising:

- Any AE
- Any TEAE
- Any Non Serious TEAE
- Intensity of TEAEs (Severe, Missing, Moderate, Mild)
- Causality of TEAEs (Related, Unknown/Missing, Not related)
- Causality and intensity of TEAEs (Related and Severe, Related and Missing, Related and Moderate, Related and Mild, Missing and Severe, Missing and Missing, Missing and Moderate, Missing and Mild, Not related and Severe, Not related and Missing, Not related and Moderate, Not related and Mild)

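### The alternative-cause exclusion lets cerebral palsy, which every child has, remove new or worsened events from the remote-spread AESI tables, and no count of search hits before that review is planned

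*SAP*

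**What the plan says.** Protocol 10.1.4 defines AESIs as adverse events suggesting possible remote spread of the toxin or hypersensitivity, and defers the terms to the SAP: "A list of preferred terms of AESIs is provided in the Statistical Analysis Plan". It has the sponsor examine these events further. Alternate aetiology, injection site and timing are to be considered; removal from outputs is not mentioned.

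SAP 8.4 supplies the remote-spread list, which "has been defined to identify any events which may possibly represent a remote spread of effect". SAP 3.2.3.1 states how it is used. Treatment-emergent events that match are "medically evaluated during the study, before the database lock and unblinding, by the sponsor". The first exclusion ground begins: "Cases will be excluded if they are confounded by presence of alternative clinical etiologies (medical history, concomitant medication or diagnosis which could account". The other grounds are a local effect, implausible timing, and exclusion "due to insufficient information/evidence to make an assessment". The section then restricts the outputs: "In the TLFs, only the final list of AESIs confirmed by the sponsor" is to be used.

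On the disease, protocol 2.1 says of CP: "The negative phenomena are muscle weakness, impaired motor control, loss of skilled movements and easy fatigability". It also names disturbed communication as a frequent accompaniment. Protocol section 8 has the baseline evaluation record this item: "The presence of spastic hemiparesis, paraparesis, diparesis, or tetraparesis". SAP 3.2.8.1 places type of paralysis under medical and surgical history.

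**The concern.** The exclusion test asks whether history or a diagnosis is able to explain the event. It does not ask whether that explanation is more likely than the toxin. One diagnosis is present in every child, and several search terms describe signs that the documents attribute to it. The SAP does not say how to treat a new or worsened event whose only alternative cause is CP.

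Long-term safety is the secondary objective, and protocol 10.1.4 describes remote spread affecting swallowing or breathing as potentially life threatening. In Cycle 1, randomisation already balances the disease background between 2, 8 and 16 U/kg. Removing cases one at a time because the disease might explain them adds little to that comparison and costs cases. The term list exists to gather scattered preferred terms into one count per child. After the exclusions, the only grouped count left is the confirmed one.

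**Working it through.** The documents give no AESI rate, no retained share and no power for AESIs, so there is no planned figure to reproduce. The check has a textual part and an illustrative part.

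**Overlap of terms.** About 53 terms in SAP 8.4 are legible. The following match CP features named in protocol 2.1, protocol section 8 or SAP 3.2.8.1:

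- weakness: Muscular weakness;
- paresis or paralysis: Hemiparesis, Monoparesis, Quadriparesis, Paresis, Paralysis;
- communication: Dysarthria, Speech disorder.

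That is 8 terms, and 8/53 = 15%. The matching is by judgement. Most of the remaining terms (ocular, cranial nerve, autonomic, respiratory) are not named in the documents as features of CP.

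**The two rules side by side.** Under protocol 10.1.4, events are identified from the list and then assessed, with alternate aetiology one of several considerations. Under SAP 3.2.3.1, events are identified from the list, and those with a possible alternate aetiology leave every AESI table and listing. The visible part of SAP section 5 does not list this as a change from the protocol. The readable text of SAP 3.2.3.1 plans no table of search hits before the review.

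**What exclusion does to the counts.** Let k be the share of hits retained, the same in each arm because the reviewers are blinded. Inputs:

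- n = 70 per arm (protocol 11.3);
- raw rates of children with at least one hit: 4% at 2 U/kg and 15% at 16 U/kg (assumed);
- an excess of at least 4 children as the mark of a visible signal (assumed).

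With X ~ Bin(70, 0.04k) and Y ~ Bin(70, 0.15k) independent, the expected counts are 70 × 0.04k and 70 × 0.15k, and the quantity of interest is P(Y − X ≥ 4).

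| Hits excluded | k | Expected children, 2 v 16 U/kg | P(excess ≥ 4) |
|---|---|---|---|
| none | 1.00 | 2.8 v 10.5 | 89% |
| 15% | 0.85 | 2.4 v 8.9 | 83% |
| 30% | 0.70 | 2.0 v 7.4 | 74% |
| 50% | 0.50 | 1.4 v 5.2 | 54% |

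The expected ratio stays at 0.15/0.04 = 3.75 in every row; only the counts fall. The 15% row is what would follow if hits were spread evenly over the terms and every hit on an overlapping term were excluded. The 30% and 50% rows allow the overlapping terms to be commoner than that.

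**Second set of assumed rates.** For 5% v 20%, 70 per arm, the power of a two-sided 5% comparison of proportions is 77% with all hits kept and 45% with half kept. The SAP plans no such test; the figures only show that the direction does not depend on the first choice of rates.

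**The case against.** The defence has several sound points.

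- **Blinding.** The review is finished before unblinding, so it should not favour an arm. This stands: the cost is lost sensitivity, not bias in the dose comparison.
- **Only treatment-emergent events enter.** Stable signs of CP are largely filtered out first, and protocol 2.1 describes CP as nonprogressive. A medically trained reviewer need not accept it as the cause of something new. This also stands. A reader might infer that the exclusion condition is met automatically by every child. The documents do not support that, because they prescribe medical evaluation and not a mechanical match, and a child with hemiparesis does not have quadriparesis by history. But the filter also means that the events reaching review are new, worse or newly judged drug-related. For these a lifelong diagnosis is a weak reason for removal, and the SAP gives no guidance.
- **Nothing leaves the database.** Excluded events remain in the adverse event listings and in the general TEAE tables by system organ class, preferred term and dose. This is correct, but they sit on separate preferred-term rows, and the number of children with any hit cannot be obtained by adding rows.
- **The departure from the protocol is partial.** Protocol 10.1.4 also has the sponsor weigh alternate aetiology, site and timing. This is fair. What the SAP adds is removal from outputs.

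Two stronger remedies might also be inferred: that CP may never count as an alternative cause, and that hypersensitivity hits need the same treatment. Neither follows. The first would override case-level medical judgement; the second concerns a separate standard query to which the CP overlap does not apply.

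**Conclusion.** The point holds as a loss of sensitivity in the AESI tables. Blinded reviewers following SAP 3.2.3.1 as written can exclude new or worsened events on about 8 of some 53 terms because of a disease common to all arms, and the readable plan has no grouped count that would show how many were removed. Under the assumed rates, the chance of a visible excess falls from 89% to between 83% and 54% when 15% to 50% of hits are excluded. Those figures rest on assumed rates, an assumed threshold and exclusion unrelated to arm.

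A reader might go further and expect AESI tables that are nearly empty at any dose. That would need something like 75% to 90% of all hits to be put down to CP (the same calculation then gives 18% and 2%). No passage supports losses of that size, so they are a worst case only. The table and listing indexes in the SAP are redacted, so a table before review may exist there, although the text does not describe one. I rate this as a cheap improvement.

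**What to change.** In SAP 3.2.3.1, keep the sponsor-confirmed AESI tables as they are. Add one set of tables, for Cycle 1 and for each later cycle by dose group, giving:

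- the number and percentage of children with any TEAE matching the 8.4 list before adjudication;
- beside it, the number confirmed;
- the number excluded by reason, with CP as the only alternative cause shown as its own category.

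Reconcile SAP 3.2.3.1 with protocol 10.1.4, either by stating that exclusion applies only to the confirmed tables or by declaring the change in SAP section 5.

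The cost is one extra table set from events the search already identifies, plus recording the exclusion reason during the blinded review. The downside is small: the table before review will contain some disease-related events. These are expected to be balanced across the randomised Cycle 1 arms. In later cycles doses can be adapted to response and tolerability, so the same table is descriptive there.
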